5. SELECTION AND WITHDRAWAL OF PATIENTS

5.1. Inclusion Criteria

Each patient must meet all of the following inclusion criteria to be eligible for enrollment in the study:

1. Males \geq 12 years of age.
2. Severe hemophilia A or B without inhibitors evidenced by:
 - a. A central laboratory measurement or documented medical record evidence of FVIII $<$ 1% or FIX level \leq 2% at Screening.
 - b. On-demand use of factor concentrate to manage bleeding episodes for at least the last 6 months prior to Screening, and meet each of the following criterion:
 - Nijmegen modified Bethesda assay inhibitor titer of $<$ 0.6 BU/mL at Screening
 - No use of BPAs to treat bleeding episodes for at least the last 6 months prior to Screening
 - No history of immune tolerance induction therapy within the last 3 years prior to Screening
3. A minimum of 6 bleeding episodes requiring factor concentrate treatment within the last 6 months prior to Screening.

-
4. Willing and able to comply with the study requirements and to provide written informed consent and assent in the case of patients under the age of legal consent, per local and national requirements.

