7.2. Efficacy Assessments

Bleeding Episode Definitions

A bleeding episode is defined as any occurrence of hemorrhage that requires administration of factor concentrates or BPA infusion, eg, hemarthrosis, muscle, or mucosal bleeding episodes. Since bleeding episodes are recorded as an efficacy assessment of fitusiran, these will not be treated as AEs unless they meet any of the SAE criteria listed in Section 7.5.6.1.

The definition of bleeding episode types described below is based on consensus opinion of International Society on Thrombosis and Hemostasis (ISTH) as reflected in a recent publication.[10]

The start time of a bleeding episode will be considered the time at which symptoms of a bleeding episode first develop. Bleeding, or any symptoms of bleeding at the same location, that occurs within 72 hours of the last injection used to treat a bleeding episode at that location will be considered a part of the original bleeding event, and will count as one bleeding episode towards the ABR. Any bleeding symptoms that begin more than 72 hours from the last injection used to treat a bleeding episode at that location will constitute a new bleeding event.

A spontaneous bleeding episode is a bleeding event that occurs for no apparent or known reason, particularly into the joints, muscles, and soft tissues.

A joint bleeding episode is characterized by an unusual sensation in the joint (“aura”) in combination with 1) increasing swelling, or warmth over the skin over the joint, 2) increasing

pain, or 3) progressive loss of range of motion or difficulty in using the limb as compared with baseline.

A muscle bleed may be characterized by pain, swelling and loss of movement over the affected muscle group.

A target joint is defined as a joint where 3 or more spontaneous bleeding episodes in a single joint within a consecutive 6-month period has occurred; where there have been ≤ 2 bleeding episodes in the joint within a consecutive 12-month period the joint is no longer considered a target joint.

A traumatic bleeding episode is one that is caused by a known injury or trauma. Bleeding episodes sustained during sports and recreation will be counted as traumatic bleeding episodes, but patients will be asked to indicate in the eDiary that the event occurred during such activities. Training will be provided on this and other aspects of eDiary use (see Section 7.2.1).

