4 PATIENT POPULATION

The populations (analysis sets) are defined as follows:

- Intent-to-treat (ITT) Analysis Set: All randomized patients. All by-treatment analyses based on the ITT analysis set will be performed according to the randomized treatment arm. Efficacy Analyses will be conducted using the ITT Analysis Set unless otherwise specified.
- Safety Analysis Set: All patients who received at least 1 dose of study drug or were randomized to on-demand arm. All by-treatment analyses based on the safety analysis set will be according to the actual treatment received. Safety Analyses will be conducted using the Safety Analysis Set unless otherwise specified.
- Per-protocol Analysis Set: All patients in the ITT set who do not have protocol deviations in the following categories:
 - Failure to meet key eligibility criteria, which will be identified prior to database lock.
 - Actual treatment differs from IRS treatment assignment
 - Prophylactic use of factor
 - Other protocol deviations that might significantly affect the completeness, accuracy, and/or reliability of the bleeding data.

The major or critical detail deviations included are as follows.

- The subject is not male and/or is younger than 12 years, but the subject was randomized.
- The subject does not have severe hemophilia A or B without inhibitors as evidence by:
 - A laboratory FVIII level $<1\%$ or FIX level $\leq 2\%$ at Screening.
 - On-demand use of factor concentrate to manage bleeding episodes for at least the last 6 months prior to Screening, or meeting one of the following criteria:
 - Nijmegen-modified Bethesda assay inhibitor titer of <0.6 BU/mL at Screening,
 - No use of bypassing agents to treat bleeding episodes for at least the last 6 months prior to screening
 - No history of immune tolerance induction therapy within the last 3 years prior to Screening,but the subject was randomized.
- The subject does not have a minimum of 6 bleeding episodes requiring factor concentrate treatment within the last 6 months prior to Screening, but the subject was randomized.
- The subject has known co-existing bleeding disorders other than hemophilia A or B, but the subject was randomized.
- The subject currently uses factor concentrates as regularly administered prophylaxis designed to prevent spontaneous bleeding episodes, but subject was randomized.

- The subject's actual treatment differs from randomization group.

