6.3.1 Primary endpoint

6.3.1.1 Primary efficacy analysis based on on-treatment strategy

The primary objective of this study is to assess the efficacy of fitusiran on prevention or reduction of bleeding. Including bleeding events in the period of intercurrent events such as use of prophylactic medication or surgery or after fitusiran treatment discontinuation could significantly bias fitusiran effect and make the comparisons difficult to interpret. The on-treatment strategy is considered of greatest relevance in assessing this primary objective (ICH E9 (R1), 2018). The primary efficacy analysis population will be the ITT Analysis Set as defined in [Section 4](#).

Global Protocol

The number of bleeding episodes will be annualized for each patient using the following formula:

$$\text{Annualized bleeding rate (ABR)} = \frac{\text{total number of bleeding episodes}}{\text{total number of days in the respective period}} \times 365.25.$$

The primary efficacy analysis will include all bleeding episodes occurring in the efficacy period.

Let λ_F represent the ABR for fitusiran arm and λ_O represent the ABR for on-demand arm. The null and alternative hypotheses of the primary analysis, respectively, can be written as follows:

$$H_0: \frac{\lambda_F}{\lambda_O} = 1 \quad H_A: \frac{\lambda_F}{\lambda_O} \neq 1$$

An estimated ABR ratio $\frac{\lambda_F}{\lambda_O} < 1$ and two-sided p-value < 0.05 from the significance test will lead to the rejection of H_0 in favor of H_A ; it will be concluded that prophylactic use of fitusiran reduces the frequency of bleeding episodes compared to the on-demand therapy.

The ABR ratio λ_F/λ_O will be estimated using a negative binomial model:

$$\begin{aligned} & \log(\text{number of bleeding episodes}) \\ &= \beta_0 + \beta_1 \cdot \text{Treatment} + \beta_2 \cdot \text{ABR}_0 + \beta_3 \cdot \text{Hemophilia type} + \log(\text{duration}). \end{aligned}$$

The number of bleeding episodes is the response variable. The treatment arm, randomization strata of number of bleeding episodes in the 6 months prior to study entry (ABR_0) and randomization strata of hemophilia type are treated as fixed effects. The logarithm of the duration (in years) that each patient spends in the efficacy period matching the bleeding episode data being analyzed is included as an offset variable to account for unequal follow-up time due to early withdrawal, surgery, etc.

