4. Each 100 imputed datasets will then be analyzed using the same negative binomial regression model. Estimates from the model such as least squares means and standard errors are then combined across imputation datasets using Rubin's formula, as implemented in the MIANALYZE procedure. These and their 95% confidence interval limits are then exponentiated to obtain the estimate of ABR for each arm and the estimate of the ABR ratio and associated p-value.

MAR and CR approaches are described below:

1. Missing at Random (MAR) Approach: Post-withdrawal missing bleeding events in both fitusiran arm and on-demand arm will be imputed under the randomized arm.
2. Copy Reference (CR) Approach: The expected ABR for a patient in the fitusiran arm both pre- and post-withdrawal is assumed to be the same as that in the on-demand arm. This accounts for a gradual loss of fitusiran effectiveness post-withdrawal. If a patient in fitusiran arm has more events pre-withdrawal than expected if this patient had been in the on-demand arm, then this 'positive residual' will feed through into a higher than expected ABR in the post-withdrawal period. This is because this patient's earlier observed ABR higher than mean event rate suggests the patient has a higher propensity to have events. Post-withdrawal data in the on-demand arm are imputed under randomized arm (assumes MAR approach).

The efficacy analysis based on treatment policy strategy may serve as sensitivity analyses for the primary efficacy analysis based on on-treatment strategy. It is important to note that the estimand based on on-treatment strategy (the primary efficacy analysis) is considered most relevant and applicable in assessing and reporting clinical efficacy of fitusiran vs. on demand treatment.

Per-protocol analysis

Efficacy analysis will be repeated on the per-protocol analysis set as defined in [Section 4](#).

Zero-inflated negative binomial model

To address the concern of potential excessive zero bleeding events, the above on-treatment and treatment policy efficacy analyses will be repeated using the zero-inflated negative binomial model and the results will be presented if model converges.

Covid-19 related sensitivity analysis

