6.3.3.5 Number of target joint bleeding episodes

A target joint is defined as a joint where 3 more spontaneous bleeding episodes in a single joint within a consecutive 6-month period have occurred. The target joints are identified at baseline and their bleeding episodes are captured and monitored during the study. An exploratory analysis of the number of target joint bleeding episodes may be performed using the same negative binominal model as the primary analysis.

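### The target-joint bleed analysis would count patients without a baseline target joint as certain zeros, which costs precision and dilutes the arm-level rates but does not bias the rate ratio

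*SAP*

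**What the plan says.** The number of target joint bleeds is an exploratory endpoint (Protocol 3.3, SAP 3.2.1). SAP 6.3.3.5 fixes which joints count: "The target joints are identified at baseline and their bleeding episodes are captured and monitored during the study". It then says that an analysis of the "number of target joint bleeding episodes may be performed using the same negative binominal model as the primary analysis".

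That section names no analysis set. SAP Section 4 supplies the default: "Efficacy Analyses will be conducted using the ITT Analysis Set unless otherwise specified". The borrowed model is run on the same set, since SAP 6.3.1.1 states: "The primary efficacy analysis population will be the ITT Analysis Set as defined in" Section 4. The fixed effects in that model are given as "The treatment arm, randomization strata of number of bleeding episodes in the 6 months prior to study entry" and the hemophilia-type stratum, with log duration as offset. No term carries target-joint status.

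Eligibility (Protocol 5.1) asks for "A minimum of 6 bleeding episodes requiring factor concentrate treatment within the last 6 months prior to Screening". The definition in Protocol 7.2 is narrower (final verb left off here): "A target joint is defined as a joint where 3 or more spontaneous bleeding episodes in a single joint within a consecutive 6-month period has".

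**The concern.** Six treated bleeds of any cause and site qualify a patient for the trial. Six traumatic bleeds, or bleeds spread over several joints, leave that patient with no target joint. Because 6.3.3.5 fixes target joints at baseline, such a patient cannot have the event, yet under the ITT default he enters with full person-time and a certain zero. The model then sees a mixture of patients who can and cannot have the event, and its single dispersion parameter has to absorb that mixture.

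Nothing else in the SAP deals with this. The zero-inflated model in 6.3.1.2 is introduced with "To address the concern of potential excessive zero bleeding events, the above on-treatment and treatment policy efficacy analyses will be repeated", which refers to the bleeding-rate analyses described before it, and 6.3.3.5 does not take it up. Target-joint status is also absent from the baseline disease characteristics listed in SAP 6.2, so a reader could not see how many patients per arm were at risk.

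At stake are the precision of one exploratory comparison and the meaning of its arm-level rates, which would be averaged over patients who cannot bleed in a target joint.

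**Working it through.** **1. The plan's own figure.** No figure is stated for the target-joint analysis. For the primary endpoint (SAP 5.1) the inputs are means 18 and 4, SDs 14 and 6, and 32 and 64 evaluable patients.

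- Var(log RR) = 14²/(18² × 32) + 6²/(4² × 64) = 0.0189 + 0.0352 = 0.0541, so SE = 0.2325.
- |log(4/18)| = 1.504, and 1.504/0.2325 = 6.47. Two-sided power at 0.05 is above 99.9%, consistent with the stated value of more than 90%.
- 96/(1 − 0.20) = 120, as stated.

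**2. Inputs for the target-joint check.** From the documents: 40 on-demand and 80 fitusiran patients (120 at 2:1), and Day 29 to Day 246, which is 218 days or t = 0.597 years. Dispersion comes from the planning SDs, k = (SD² − mean/t)/mean²:

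- on-demand: (196 − 30.16)/324 = 0.512
- fitusiran: (36 − 6.70)/16 = 1.831

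Assumed, because the documents are silent: p, the share of patients with a baseline target joint, and the target-joint bleed rate among them, taken as 30-60% of the planning rates.

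**3. Closed form.** Let μ be the expected target-joint count in an at-risk patient.

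- At-risk subset: Var(log RR) = sum over arms of (1/μ + k)/(np)
- All ITT: the same, plus sum over arms of (1 − p)/(np)

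The extra term is positive whenever p < 1. Example with p = 0.5 and 60% of planning rates:

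- μ = 18 × 0.6 × 0.597 = 6.45 on-demand, and 4 × 0.6 × 0.597 = 1.43 fitusiran
- Subset: (0.155 + 0.512)/20 + (0.698 + 1.831)/40 = 0.0334 + 0.0632 = 0.0966, SE 0.311
- All ITT: add 0.5/20 + 0.5/40 = 0.0375, giving 0.1341, SE 0.366
- Ratio of SEs: 0.366/0.311 = 1.18

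The arm-level rates halve, from 10.8 and 2.4 per year to 5.4 and 1.2. The ratio is 0.222 either way.

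**4. Simulation without covariates or drop-out.** 1,000 trials per scenario, with the negative binomial model fitted both ways. Entries are all-ITT relative to the subset; ranges cover 30% and 60% of planning rates.

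| p | Closed-form SE ratio | Sampling SD ratio | Model SE ratio | Fitted k, all ITT | Fitted k, subset |
|---|---|---|---|---|---|
| 0.3 | 1.20-1.24 | 1.19-1.26 | 1.39-1.53 | 7.0-8.6 | 0.67-0.83 |
| 0.5 | 1.14-1.18 | 1.16-1.21 | 1.29-1.40 | 3.4-4.2 | 0.71-0.87 |
| 0.7 | 1.09-1.11 | 1.09-1.15 | 1.18-1.24 | 1.9-2.3 | 0.77-0.91 |
| 0.9 | 1.03-1.04 | 1.03-1.04 | 1.06-1.09 | 1.1-1.3 | 0.79-0.92 |

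The median rate ratio was 0.21-0.22 in both analyses (true value 0.222). With a common k of 0.5 and 50% of planning rates, the sampling SD ratio was 1.36, 1.26, 1.15 and 1.07 for p = 0.3, 0.5, 0.7 and 0.9, and the model SE ratio 1.62, 1.45, 1.28 and 1.09.

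**5. Simulation with both stratification terms in the model.** 40 versus 80 patients, 218 days, p from 0.4 to 0.8. The rate ratio was again unchanged. All-ITT gave a sampling SD of log RR about 7-33% larger and a model SE about 9-42% larger.

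**6. Coverage of nominal 95% Wald intervals.** Without covariates it was about 94-97% for all ITT and 92-96% for the subset. With the stratification terms it was about 90-94% for the subset.

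**The case against.** Several points on the other side stand.

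- **The population is inferred.** SAP 6.3.3.5 borrows a model and does not name a set, and its sentence about following target joints could be read as covering only patients who have them. A reader might infer that the SAP expressly places the other patients in this analysis. It does not; that follows from the Section 4 default. If a subset was intended, 6.3.3.5 still needs to say so.
- **All-ITT is a legitimate analysis.** A reader might infer that the planned analysis is biased or pointless. Neither is supported: certain zeros occur in both randomized arms, the rate ratio is right on average, and target-joint bleed burden in the whole trial population is a valid quantity. Keeping everyone follows the stated default.
- **The protocol definition is dynamic.** Under Protocol 7.2 a joint can gain or lose target status over time, and 218 days is long enough to gain it. That a patient cannot have the event rests on the baseline rule in SAP 6.3.3.5.
- **Not all of the narrowing is real precision.** The model SE falls by more than the sampling SD, and restricted Wald intervals can under-cover slightly. The rise in sampling SD is the better measure of the true loss.
- **The subset may be thin.** At p = 0.4 it is about 16 versus 32 patients. With about 26 hemophilia B patients planned, the on-demand arm would keep some 26 × 1/3 × 0.4 ≈ 3.5 of them, so convergence is not assured.

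These points limit the size and importance of the concern. They do not remove the loss of precision or the undefined at-risk population.

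**Conclusion.** The point holds as a minor one about precision and clarity. Read with the ITT default, SAP 6.3.3.5 would include patients who cannot have the event. The direction of the loss is certain for any share below 100%. Its size depends on a share that the documents do not give: over an assumed 40-80% it is roughly 7-33% in the sampling SD of the log rate ratio and roughly 9-42% in the width of the model-based interval. These two ranges measure different things and should not be interchanged. At 90% the loss is only about 3-9% across both measures. The event rates and dispersion in the checks are also assumptions, the latter mostly derived from the planning SDs for all bleeds.

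The analysis is optional and lies outside the testing hierarchy in SAP 5.7, so no alpha and no primary or secondary conclusion depends on it.

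**What to change.** State in SAP 6.3.3.5 that the negative binomial model, with the same offset and stratum terms, is fitted in ITT patients who have at least one target joint at baseline. Target-joint status is set before treatment, so this restriction keeps the randomized comparison. In the same place:

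- report the number of such patients by arm;
- keep the all-ITT result as supportive;
- give descriptive statistics only if the model does not converge, as SAP 6.3.3.4 already does for Haemo-QOL.

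The cost is one or two sentences and one line in a baseline table. No new data are needed, because 6.3.3.5 already has target joints identified at baseline. The downside is a smaller sample and possible slight under-coverage of the Wald interval, which is a reason to show the all-ITT result alongside.

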6.3.3.6 HJHS

Joint health status will be assessed via the HJHS, as administered by a healthcare professional trained in the use of anthropometric measures. Response will be summarized. If the joint score is evaluated with 2 weeks after a joint or adjacent muscle bleeding episode or a surgery is performed on a joint and the joint score is evaluated from start date of surgery to the end of perioperative

procedure period + 7 days, then the data for that joint will be excluded. A sensitivity analysis excluding the non-evaluable results will be performed.

6.3.3.7 Annualized weight-adjusted consumption of factor concentrates

Factor concentrate dose will be recorded by the patient in the eDiary and reviewed by the Investigator (and Sponsor or delegate) for the study duration to assess on-demand factor concentrate use as treatment of breakthrough bleeding episodes. Weight-adjusted factor usage will be calculated programmatically.

The annualized weight-adjusted factor consumption, number of factor injections per bleed/per subject, weight adjusted total dose per bleed/per subject, and results of patient-reported evaluation of effectiveness of treatment for each bleed (excellent, good, moderate or none) as assessed by both patient and caregiver (Blanchette, 2014) will be summarized by study period. Factor concentrates consumption during Day 1 to Day 8 period under standard factor concentrates regimen will be summarized as appropriate. Day 1 to Day 8 period is from Day 1 to the earlier of Day 8 and the last day of bleeding follow up. Additional summary will be provided by bleed location, causality and severity. The compliance to the bleed management guideline will be summarized after Day 8 to the end of study,

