6.3.1.2. Bleeding Episode Management Recommendations for Patients in the Fitusiran Treatment Arm

Given the mechanism of action and pharmacodynamic profile of fitusiran, the factor concentrate dose necessary to safely and effectively treat breakthrough bleeding episodes will be lower than standardly prescribed. This is supported by data from the Phase 1 study in which bleed events were managed with factor and BPA, as well as additional modeling and ex vivo spiking data.

More detailed information on the clinical experience in bleeding episode management in Phase 1 and Phase 1/2 fitusiran studies, as well as supportive nonclinical studies is provided in the Investigator's Brochure.

After administration of fitusiran, AT lowering will be progressing toward therapeutic levels. As quickly as 7 days after the initial fitusiran dose, the majority of patients will have AT levels at or below 60% residual activity. By 14 days after dosing, it is expected that 94% of patients will have AT lowering of >50%, with a median value of 66.8 %. Based on these AT kinetics, it is recommended that patients continue with their standard factor regimens for the first 7 days following initiation of fitusiran dosing, with institution of the protocol-specific bleed management guidelines with reduced factor or BPA at Day 8 and beyond ([Table 4](#)).

Patients on fitusiran, will be provided a bleed management plan with appropriate dosing of factor concentrates for use during Day 1 through 7, as well as a bleed management plan with dosing for Day 8 and beyond. Thereafter the bleed management plan will be reviewed and updated at monthly visits, and new written plans provided to the patient if dosing changes.

Importantly, during the treatment period, patients should not use factor concentrates or other hemostatic agents as prophylaxis for bleeding episode prevention, including doses related to anticipated hemostatic challenges such as physical activity. For prophylaxis of bleeding episodes in patients who require operative procedures see [Section 6.6](#).

Bleed Management Guidelines Day 1 to Day 7:

Patients should be instructed to call the site prior to administering factor or BPA. Patients should continue with their standard factor/BPA regimens.

Bleed Management Guidelines Day 8 and Beyond:

When a patient experiences symptoms that may be consistent with bleeding episodes, the following steps should be followed:

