5.2 General methods

All data listings that contain an evaluation date will contain a study day relative to the day of Day 1 visit when baseline assessments are performed and fitusiran first dose is given, which is designated as Day 1. The Day 1 visit date should coincide with randomization date but could occur within 3 days after the randomization. If the fitusiran first dose is given after Day 1 visit, a study day will be calculated relative to the day of first dose. Study days will be calculated as evaluation date – Day 1 visit date (or first dose date) + 1 and pre-Day 1 visit days will be calculated as evaluation date – Day 1 visit date (or first dose date). For example, the day prior to Day 1 visit will be Day –1 and the day after Day 1 visit will be Day 2, etc. There will be no Study Day 0.

Categorical variables will be summarized using counts and percentages. Continuous variables will be summarized using the number of patients (n), mean, SD, median, interquartile range (Q1, Q3), minimum value (min), and maximum value (max). The precision of the measurement for each continuous variable will be used to determine the number of decimal places to present in tables, figures and derived listings. Minimum and maximum values will be reported with the same precision as the units of measure. The other statistics will be reported to 1 greater decimal place, and the SD will be reported to 2 additional decimal places. Any values that require transformation to standard units (metric or SI) will be converted with the appropriate corresponding precision.

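### SAP 6.3.3.7 counts Day 8 as standard regimen and starts the guideline-compliance summary the day after, but protocol 6.3.1.2 starts reduced dosing on Day 8

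*SAP*

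**What the plan says.** **SAP 6.3.3.7** plans two summaries that depend on when the dosing regimen changes.

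- Factor use under the standard regimen: "Factor concentrates consumption during Day 1 to Day 8 period under standard factor concentrates regimen will be summarized as appropriate". The window is then defined: "Day 1 to Day 8 period is from Day 1 to the earlier of Day 8 and the last day of bleeding follow up".
- Adherence to the guideline: "The compliance to the bleed management guideline will be summarized after Day 8 to the end of study".

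**Protocol 6.3.1.2** sets the change of regimen for the fitusiran arm.

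- Standard regimen: "it is recommended that patients continue with their standard factor regimens for the first 7 days following initiation of fitusiran dosing".
- Reduced dosing: "with institution of the protocol-specific bleed management guidelines with reduced factor or BPA at Day 8 and beyond".
- Each fitusiran patient receives written plans "for use during Day 1 through 7, as well as a bleed management plan with dosing for Day 8 and beyond".
- The section has one heading for Days 1 to 7 and another that reads "Bleed Management Guidelines Day 8 and Beyond".

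**SAP 5.2** fixes the day count. The Day 1 visit is the visit at which the first dose is given, and there is no Day 0. If dosing is delayed, "If the fitusiran first dose is given after Day 1 visit, a study day will be calculated relative to the day of first dose".

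**The concern.** Day 8 falls on different sides of the boundary in the two documents. A programmer working from the SAP would report factor given on Day 8 as standard-regimen use and would begin the compliance summary on Day 9. Under the protocol, Day 8 is the first day on which the reduced-dose guideline applies.

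That day has some interest of its own. Protocol 6.3.1.2 bases the switch on antithrombin kinetics: as early as 7 days after the first dose, most patients are at or below 60% residual activity. Protocol 1.5 says that factor or bypassing-agent doses above the recommended level may raise the risk of thrombosis. A full dose given on the first day of the new plan is a natural transition error, and a compliance summary should be able to show it. At stake is the accuracy of that summary at its starting point.

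**Working it through.** The plan gives no figure to reproduce. The check compares the windows as sets of study days and then gauges scale.

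**1. Day count.** First dose is Day 1 and there is no Day 0 (SAP 5.2). The first 7 days are therefore Days 1 to 7.

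**2. Windows side by side.**

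| Window | SAP 6.3.3.7 | Protocol 6.3.1.2 | Difference |
|---|---|---|---|
| Standard regimen | Days 1 to 8 (8 days) | Days 1 to 7 (7 days) | Day 8 |
| Reduced-dose guideline / compliance | Day 9 onward | Day 8 onward | Day 8 |

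Both differences are the same single day. It is added to the first SAP window and missing from the second.

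**3. Share of each window.**
- Standard regimen: 1/8 = 12.5% of the SAP window.
- Compliance, if the end is taken as Day 246 (end of the efficacy period): 246 − 8 + 1 = 239 days under the protocol against 246 − 9 + 1 = 238 under the SAP, and 1/239 = 0.42%.
- The SAP says end of study, and the end-of-study visit is nominally Day 253. That gives 253 − 8 + 1 = 246 days, and 1/246 = 0.41%. The choice of end day makes no practical difference.

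**4. New bleeds starting on Day 8.** Inputs are 80 fitusiran patients (protocol 1.3) and planning mean annualized bleeding rates (ABR) of 4 and 18 (protocol 8.1, SAP 5.1). The Day 8 rate is not given, so the two planning means serve as an assumed range.

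Expected new bleeds = N × ABR / 365.25
- ABR 4: 80 × 4 / 365.25 = 0.88
- ABR 18: 80 × 18 / 365.25 = 3.94

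**5. What this range leaves out.** It counts new bleeds, whereas the SAP windows classify treatments. A repeat dose given on Day 8 for a bleed that began earlier would also be misassigned and is not in the count. Nor is 18 a ceiling: entry requires at least 6 treated bleeds in 6 months, and one randomization stratum has more than 10 in 6 months, which is above 20 per year.

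**The case against.** **The consequence is close to nil.** This summary is exploratory and descriptive, and the standard-regimen part is discretionary. No data are lost, because the same SAP section also summarizes factor consumption by study period, so Day 8 appears within the onset period. Patient safety does not depend on this table: under protocol 7.2.1, sites are notified of initial bleed treatments, must contact a patient whose dose exceeds the plan, and are alerted at a third dose. All of this stands, and it sets the severity. It does not make the two windows agree.

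**Day 8 may have an innocent origin.** Protocol Table 8 places the Day 8 sample at 168 hours after dosing, and 168 / 24 = 7, so seven elapsed days end during Day 8. That may explain the slip but cannot justify it. The written plans and headings in 6.3.1.2 assign the whole of Day 8 to reduced dosing.

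**It could be a deliberate change.** The change tables in SAP 2.5 and 2.6 record no change to this window. They list major changes only, so their silence supports an oversight without proving it.

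**Conclusion.** The inconsistency is real and minor. Every fitusiran-arm treatment given on Day 8 is attributed to the wrong regimen and left out of the compliance summary. That includes compliant treatments as well as excessive ones, since the guideline also covers dose intervals, calls to the site and antifibrinolytic combinations.

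The scale is about 0.9 to 3.9 new Day 8 bleeds, assuming 80 patients and the planning mean rates. It is illustrative and bounds nothing from above. The conclusion itself does not depend on those rates. It rests on the SAP 5.2 day count and on the SAP being programmed literally.

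A reader might infer two stronger points that the documents do not support.

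- **That patients would be misdosed or exposed to more thrombosis risk.** Dosing follows the written plans, which change on Day 8, and the eDiary alerts. The SAP summary governs neither. No primary or secondary endpoint, alpha or sample size is affected.
- **That the protocol contains a second dosing rule.** The synopsis, under reference therapy, mentions reduced initial doses during the efficacy period, which starts on Day 29. It does not say only then, and it does not authorize full doses on Days 8 to 28. Sections 4.1 and 6.3.1.2 give the operative rule, so this is summary wording that could be tidied.

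**What to change.** In SAP 6.3.3.7:

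1. End the standard-regimen window at Day 7 or at the end of bleeding follow-up, whichever comes first, and rename it accordingly.
2. Summarize guideline compliance from Day 8 through end of study, and state that it is for the fitusiran arm, since the Day 8 switch applies only there.

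As an editorial note, the synopsis sentence on reduced doses could refer to Day 8 onward in place of the efficacy period.

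The cost is two window boundaries and, optionally, one synopsis phrase. No new data are needed: factor doses are already recorded in the eDiary and study day is already derived under SAP 5.2.
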